
## **Study Design**

### **Phase\***

Not applicable

### **Design**

This study will be conducted as a randomized, blinded study among patients requiring short-term indwelling transurethral catheterization following pelvic reconstructive surgery.

### **Study duration**

RECRUITMENT We plan to recruit women from 5 sites in 3 departments in the University of Pennsylvania Health System: 1) Urogynecology at Hospital of University of Pennsylvania (HUP), 2) Urogynecology at Pennsylvania Hospital (PAH) and 3) Urology at Pennsylvania Hospital (PAH). Last year, the combined surgical volume of these cases at our three clinics was 532 subjects; thus, we anticipate we will be able to easily recruit and collect data from the proposed sample size of 144 (72 participants per arm) in about eight months. FOLLOW UP VISITS: Patients will follow up for a total of 6 weeks after surgery through three weekly follow-up calls and one 6-week postoperative visit. Urogynecology nurses will contact study participants once a week for the first three weeks following surgery per routine practice in our offices. Six weeks following surgery, patients will return to the office for a routine post-operative assessment with the investigating physicians. PROJECT DATES Research Proposal March 2014 IRB Approval August/September 2014 Data Collection September 2014 - September 2015 Data Entry November 2014 - October 2015 Data Analysis November 2015 Abstract Submission December 2015

### **Resources necessary for human research protection**

Describe research staff and justify that the staff are adequate in number and qualifications to conduct the research. Describe how you will ensure that all staff assisting with the research are adequately informed about the protocol and their research related duties. Please allow adequate time for the researchers to conduct and complete the research. Please confirm that there are adequate facilities for the research.

Key Personnel: Primary Investigator: [name] Co-Investigator, Mentor: [name], MS Co-Investigator, Mentor: [name], MBA, MSCE (Cost-effectiveness analysis) Co-Investigator, Mentor: [name], MSCE (Infectious Diseases) Co-Investigator: [name] Co-Investigator: [name] Co-Investigator: [name] Co-Investigator: [name] The above investigators, as well as the urogynecologic nurses who help with routine clinical care and will be in touch per routine care with post-operative patients, will be made informed of protocol and research-related duties through reading material as well as research meetings after the protocol is approved. Additionally, the primary investigator will be in touch with each of the support staff and co-investigators weekly to help coordinate duties, provide updates, and to answer any questions that may occur through the course of this study. The proposed clinical study is a multi-disciplinary collaboration between the Divisions of Urogynecology (OB/GYN), Urology (Surgery) and Infectious Diseases (Internal Medicine). We will recruit patients from five sites, including: the Division of Urogynecology (OB/GYN) at the Hospital of University of Pennsylvania (HUP) the Division of Urogynecology (OB/GYN) at Pennsylvania Hospital (PAH) the Division of Urogynecology (OB/GYN) at Chestnut Hill Hospital (CHH) the Division of Urology (Surgery) at Pennsylvania Hospital (PAH). the Division of Urology (Surgery) at the Hospital of University of Pennsylvania (HUP) Last year, the combined surgical volume of these cases at our three clinics was 532 subjects; thus, we anticipate we will be able to easily recruit the proposed sample size in eight months. Therefore, there should be enough time to recruit, as well as conduct and complete research, within the next year. The University of Pennsylvania Health System (UPHS) is an academic tertiary care referral center that draws patients from a wide geographic area. The four urogynecology clinics are located at the Hospital of the University of Pennsylvania, an inner city teaching hospital; Pennsylvania Hospital, a largely private urban hospital; and Chestnut Hill Hospital, a suburban community hospital. The Division of Urogynecology offices cares for the full spectrum of pelvic organ prolapse, urinary incontinence, fecal incontinence, and other pelvic floor dysfunction related disorders. The Division of Urology has female urology clinics at both the Hospital of the University of Pennsylvania and Pennsylvania Hospital, as well as inpatient services at Pennsylvania Hospital. The clinical and research infrastructure of these two hospitals are completely integrated with electronic inpatient and outpatient medical records, shared clinical responsibilities, on-call schedule. Additionally, we have a staff of clinical and research nurses to help coordinate with patient follow-up visits and routine post-operative care. No radiologic or

laboratory facilities will be used in this study. The Division of Infectious Diseases (Internal Medicine) has over 20 academic and research faculty who offer consultative services to departments conducting clinical trials and/or translation research, including extensive expertise in hospital-acquired infections and antibiotic resistance research. Clinical research facilities of the Division of Urogynecology are located in close proximity to all patient activity. Fellows have their own dedicated desk stations and a state-of-the-art computer and printer. The PC has word-processing, spreadsheet, and statistical database analysis programs (STATA). The fellows have full access to secretarial support, information services, slide preparation and poster presentations assistance, and videotaping/editing services. Each fellows computer is connected to the main hospital network, which allows for easy and rapid retrieval of inpatient data, biomedical library access, and free access to the Internet. Literature searches may be conducted from the fellows office through these means. Additionally, the Biomedical Library is in close proximity and has extensive facilities for literature searches, journals, and inter-library loan. The library periodically holds courses on updated methods of database searches, and experienced medical librarians are always on staff. The Clinical Center for Epidemiology and Biostatistics (CCEB) provides a Clinical Research Certificate Program for clinicians associated with the university and provides a foundation in biostatistics, research methodology, epidemiology and grant writing to allow those completing to coursework to have the tools to pursue a career as an independent researcher. CCEB will provide biostatistics support for this project. The CCEB has been actively involved in clinically- and pharmacologically-oriented research since 1978. As a Type II Center, it is the primary home for epidemiology and biostatistics at the University of Pennsylvania. It is an interdisciplinary and interdepartmental program of more than 275 individuals and includes clinical and non-clinical faculty, fellows, research staff, biostatisticians, and clerical staff. Many studies in the CCEB have focused exclusively on women's health issues. Additionally, should patients require additional medical services as a consequence of the research, such as adverse reactions to medications, patients will have 24-hour access to the on-call physician or to the medical offices of the co-investigators, where the patients can be examined and referred to additional medical services if necessary.

## Characteristics of the Study Population

### **Target population**

Adult patients requiring short-term indwelling transurethral catheterization for at least 24 hours following pelvic reconstructive surgery for pelvic organ prolapse, incontinence, or both.

### **Subjects enrolled by Penn Researchers**

370

### **Subjects enrolled by Collaborating Researchers**

0

### **Accrual**

This trial will be an non-inferiority trial, intended to determine if a short course of methenamine hippurate is no worse than a short course of fluoroquinolones (ciprofloxacin at Pennsylvania Hospital, levofloxacin at HUP, based on current practice and fluoroquinolone availability at each site) in prevention of post-operative UTI in short-term indwelling catheterization. Our primary outcome is the treatment of UTI by symptoms, a clinically relevant outcome. In the only study to look at this primary outcome after treatment with prophylactic antibiotics during short-term catheterization in urogynecologic surgery, the percentage of patients requiring treatment for UTIs after prophylactic antibiotics was 22%. If we assume a non-inferiority margin of 15%, a clinically relevant margin and commonly used in non-inferiority/equivalence trials for studies examining antibiotic use for urinary tract infections, as well as 80% power and a one-sided alpha of 0.025, 120 participants in each arm (total of 240 patients) will be required. Of all patients that undergo pelvic reconstructive surgery at our institution, approximately 75% are discharged home with an indwelling catheter. With a potential 15% drop-out rate, we therefore anticipate that we will need to recruit about 370 eligible patients in our clinics. As listed before, review of the surgeons logs over the last 12 months shows that this study is feasible due to the large volume of pelvic reconstructive surgery procedures in Urogynecology and Urology. Last year, the combined surgical volume of these cases at our three clinics was 532 subjects; thus, we anticipate we will be able to easily recruit the proposed sample size in one year. We plan to

recruit women from 4 sites in 3 departments in the University of Pennsylvania Health System: 1) Urogynecology at Hospital of University of Pennsylvania (HUP), 2) Urogynecology at Pennsylvania Hospital (PAH) and 3) Urology at Pennsylvania Hospital (PAH). Physician investigators are present at all three sites, and will have opportunity to screen patients planning for surgery for pelvic organ prolapse, urinary incontinence, or both, for participation.

#### **Key inclusion criteria**

Inclusion criteria: female; patients who are able to read and write English; 18 years of age or older; underwent surgery for pelvic organ prolapse, urinary incontinence, or both; require post-operative short-term transurethral catheterization for greater than 24 hours.

#### **Key exclusion criteria**

Exclusion criteria: patients undergoing surgical intervention for sacral neuromodulation, or mesh excision; patients requiring long-term catheterization secondary to injury to the urinary tract; patients who pass their post-operative trial void and thus, do not require additional catheterization; patients requiring catheterization for less than 24 hours; pregnant patients; patients who are breast-feeding; allergy to methenamine hippurate or fluoroquinolones (either ciprofloxacin or levofloxacin); impaired renal or hepatic function; pre-operative urinary retention; patients who are currently using sulfonamides; patients who have severe dehydration; patients using tizanidine; patients sensitive to quinolones class; patients using theophylline; patients with myasthenia gravis; patients with prolongation of QT interval.

#### **Vulnerable Populations**

##### **Children Form**

##### **Pregnant women (if the study procedures may affect the condition of the pregnant woman or fetus) Form**

##### **Fetuses and/or Neonates Form**

##### **Prisoners Form**

##### **Other**

**x None of the above populations are included in the research study**

#### **The following documents are currently attached to this item:**

*There are no documents attached for this item.*

#### **Populations vulnerable to undue influence or coercion**

All patients will be advised that participation in the study is completely voluntary, and does not involve any monetary compensation, which will minimize the risk of coercion for the economically disadvantaged. Patients will also be assured that their participation will not affect their care or treatment. Also, each person will be provided the opportunity to decline or participate in the study through the process of thorough informed consent. Penn employees and students who may be approached during their evaluation in the urogynecology clinics will be told that their decision to participate will not impact their standing with the University.

#### **Subject recruitment**

We plan to recruit women from 3 departments in the University of Pennsylvania Health System: 1) Urogynecology at Hospital of University of Pennsylvania (HUP), 2) Urogynecology at Pennsylvania Hospital (PAH) and 3) Urology at Pennsylvania Hospital (PAH). Physician investigators, who are present at all clinics associated with these departments, will screen patients planning for surgery for pelvic organ prolapse, urinary incontinence, or both, for participation. Patients may also be pre-screened for eligibility using the electronic medical record. Following confirmation of eligibility, the physicians will obtain informed consent preoperatively prior to surgery.

Will the recruitment plan propose to use any Penn media services (communications, marketing, etc.) for outreach via social media avenues (examples include: Facebook, Twitter, blogging, texting, etc.) or does the study team plan to directly use social media to recruit for the research?

No

**The following documents are currently attached to this item:**

*There are no documents attached for this item.*

**Subject compensation\***

Will subjects be financially compensated for their participation?

No

**The following documents are currently attached to this item:**

*There are no documents attached for this item.*

**If there is subject compensation, provide the schedule for compensation per study visit or session and total amount for entire participation, either as text or separate document**

None.

## **Study Procedures**

**Suicidal Ideation and Behavior**

Does this research qualify as a clinical investigation that will utilize a test article (ie- drug or biological) which may carry a potential for central nervous system (CNS) effect(s)?

No

**Procedures**

**RECRUITMENT** We plan to recruit women from 3 clinical sites associated with 3 departments in the University of Pennsylvania Health System: 1) Urogynecology at Hospital of University of Pennsylvania (HUP), 2) Urogynecology at Pennsylvania Hospital (PAH) and 3) Urology at Pennsylvania Hospital (PAH). Physician investigators, who are present at all sites, will screen patients planning for surgery for pelvic organ prolapse, urinary incontinence, or both, for participation. Following confirmation of eligibility, the physicians will obtain informed consent prior to surgery at the planned preoperative visit. Last year, the combined surgical volume of these cases at our three clinics was 532 subjects; thus, we anticipate we will be able to easily recruit the proposed sample size in twelve months. **ENROLLMENT AND BASELINE VISIT:** Patients who are being discharged home with an indwelling catheter following pelvic reconstructive surgery will be enrolled into the study. With regards to outpatient surgery (such as a suburethral sling), this will occur within a few hours after surgery for patients who fail their trial of void. Following inpatient surgery (such as sacrocolpopexy, uterosacral or sacrospinous ligament fixation, or colpocleisis), patients who are being discharged from the hospital with an indwelling catheter will be enrolled into the study. As per standard of care, all subjects will be scheduled for an office visit for catheter removal 24 to 72 hours after placement of the indwelling catheter per surgeon preference. Demographic information will be collected from the patients medical record (age, menopausal status, concurrent estrogen use, ethnicity, level of education, medical comorbidities, history of recurrent UTIs, and duration of hospitalization). Data regarding the patients surgical intervention (procedure type, surgical complications, operative time) will be collected from the operative record. At the time of catheter removal, subjects will be randomized to either methenamine hippurate or fluoroquinolones, using sealed, opaque, sequentially numbered envelopes. All patients, and all physicians and nurses directly involved in patient calls and clinical interaction, will be masked to treatment allocation. Only the nurses involved in catheter removal, but not decisions on the primary outcome, will open the envelope, and distribute the allocated medication to the patient, who will take one dose at the office. A 24-hour course of fluoroquinolones, as per AUA guidelines, are the first-line antibiotics for catheter removal, and will be one of the active arms of the study. Due to differences of office practice and formulary availability, the fluoroquinolone of choice at each site will be different; this is clinically relevant as different urology practices across the country use different fluoroquinolones for prophylaxis. At HUP and Radnor, the 24 hour course of fluoroquinolone used will be one dose of 500 mg of levofloxacin, as per office practice and formulary availability. At the other sites (Pennsylvania Hospital, Chestnut Hill Hospital), the 24 hour course of fluoroquinolone as per office practice will be two doses of 500 mg of ciprofloxacin, 12 hours apart. Methenamine hippurate will be given as two doses of 1g of methenamine hippurate, taken 12 hours apart. The patient will not be told which

medication they are taking. The methenamine, ciprofloxacin, and levofloxacin used in this study are all similar in shape, although not in color. Following catheter removal one to two hours after the first dose of medication, patients will be given a white vial or bag with the second dose of medication (if given methenamine or ciprofloxacin) and will be instructed to take second dose of the study medication at home about 12 hour later. As part of standard of care, nurses perform void trials per practice guidelines by backfilling the bladder with 300 cc normal saline, removing the catheter, and prompting the patient to void immediately. If a patient fails her trial of void, majority of the patients at our site are taught intermittent self-catheterization. If an indwelling catheter is replaced, the allocated treatment (drug or placebo) will be re-administered at repeat trial of void/repeat catheter withdrawal. No further drug will be given if the patient performs intermittent self-catheterization after the failed trial of void. FOLLOW UP VISITS: Three weekly follow-up calls and one postoperative visit are planned. It is standard of care of our clinical practices in the office for a clinical urogynecology nurses to routinely contact patients post-surgery to ask about any symptoms or complications from the procedures they underwent. In this study, per routine office practice, urogynecology nurses will call study participants once a week for the first three weeks following surgery. As per routine, using a structured form, patients will be asked about symptoms of UTI, any treatment for UTI, any urine laboratory testing, visits, and treatment for suspected UTI from other providers other than the urogynecology clinic (e.g. ER, primary care doctor), treatment of complications secondary to UTI (such as pyelonephritis and sepsis), and any additional use of antibiotic for infections other than UTI. Questions related solely to the study medication will include compliance with medications given, and side effects within 24 hours of taking medication. At any time during the study, as per standard of care of all urogynecology patients, patients who feel that they may have UTIs will be encouraged to call the urogynecology clinical nurses or the on-call physician with their symptoms. These encounters, any testing, and any empiric treatment are documented in the electronic medical system. If the diagnosis of UTI is unclear at any time, per standard of care, the patient will be asked to come into the office for physical examination and further diagnostic testing. If patients are suspected of having UTI, treatment for UTI will be initiated. As per routine office care for treatment of UTI, if possible, all patients will be asked to give a specimen for urinalysis and urine culture prior to beginning empiric treatment. Four to eight weeks following surgery, as per standard of care, patients will return to the office for a routine post-operative assessment with the investigating physicians. The patients will undergo routine post-operative physical examination and answer the above questions. Any methenamine or ciprofloxacin that has not been taken as instructed will be returned at this time. At their post-operative visit, the patient will be asked if they were aware of which medication they were taking to assess blinding.

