**Processing of Materials\***

Will the research involve processing (such as over encapsulating, or compounding)?

Yes

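### Masking is not secured for a symptom-and-treatment primary outcome: the drugs differ in colour, callers ask about the second dose, and the only check of the blind comes at 4 to 8 weeks

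*Combined protocol and SAP*

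**What the plan says.** Procedures makes a broad claim: "All patients, and all physicians and nurses directly involved in patient calls and clinical interaction, will be masked to treatment allocation". The exception is narrow: "Only the nurses involved in catheter removal, but not decisions on the primary outcome, will open the envelope, and distribute the allocated medication". The patient is not told her drug.

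The same section then says of the products: "The methenamine, ciprofloxacin, and levofloxacin used in this study are all similar in shape, although not in color". The first dose is swallowed in the office, with no concealment described. For the home dose, "patients will be given a white vial or bag with the second dose of medication (if given methenamine or ciprofloxacin"; levofloxacin, used at HUP and Radnor, is a single dose.

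The weekly calls in the first three weeks cover UTI symptoms, UTI treatment and compliance with the study medication (Procedures). Secondary outcome variable(s) says the compliance question concerns the second dose.

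Primary outcome variable(s) counts a patient who is given antibiotics for a UTI suspected on two or more listed symptoms, without vaginal symptoms, in the three weeks after surgery. A positive culture is not needed.

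At the visit four to eight weeks after surgery (six weeks in Study duration): "Any methenamine or ciprofloxacin that has not been taken as instructed will be returned at this time". Also: "At their post-operative visit, the patient will be asked if they were aware of which medication they were taking to assess blinding".

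The form asks, under Processing of Materials and again under In-House Manufacturing of Materials: "Will the research involve processing (such as over encapsulating, or compounding". Both are answered Yes. Procedures mentions no such step.

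**The concern.** Both parts of the primary outcome, what the patient reports and whether a clinician prescribes, are open to influence from knowing the arm. A woman or caller who believes the drug was the non-antibiotic may report, probe or treat at a different threshold. The shift could go either way. Over-recording in the methenamine arm would make a truly non-inferior drug look worse. Under-recording would make a truly inferior one look acceptable.

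The described procedures leave two routes open during the outcome window: the visible colour, and a conversation about the second dose held by the people who collect the outcome. The single late question cannot show whether either route was used. By then a woman treated for UTI may guess her drug from that result, and failed masking cannot be told apart from a treatment effect.

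**Working it through.** **1. Timing.** The outcome window closes at 3 × 7 = day 21. The return of leftovers and the masking question fall between 4 × 7 = day 28 and 8 × 7 = day 56, which is 7 to 35 days after the window closes. The three weekly calls fall inside the window.

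**2. What the second-dose question can reveal, by site.**

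| Site type | Methenamine arm | Fluoroquinolone arm | Does having a home dose separate the arms? |
|---|---|---|---|
| Ciprofloxacin sites | home dose | home dose | No; colour only |
| Levofloxacin sites | home dose | none described | Yes, if the caller knows the local regimen |

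That a caller knows the clinic's regimen is an inference, but a modest one: the protocol says the choice of fluoroquinolone follows office practice at each site.

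**3. The plan's own sample size.** Inputs from Accrual: 22% in the fluoroquinolone arm, margin 15%, 80% power, one-sided alpha 0.025. I take equal true rates and an absolute margin.

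n = (1.960 + 0.842)² × 2 × 0.22 × 0.78 / 0.15² = 7.849 × 0.3432 / 0.0225 = 119.7, so 120 per arm. This reproduces the stated figure and supports reading the margin as 15 percentage points.

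**4. Effect of an assumed shift b, in the methenamine arm only.** The documents give no value for b; 1 to 3 points is an illustrative range. With pC = 0.22 and pT the recorded methenamine rate:

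SE = √{[pC(1 − pC) + pT(1 − pT)] / 120}

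P(non-inferiority declared) = Φ{[0.15 − (pT − pC)] / SE − 1.960}

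*Equal true rates, 2 points over-recorded.* pT = 0.24, SE = √[(0.1716 + 0.1824)/120] = 0.0543. Power = Φ(0.13/0.0543 − 1.960) = Φ(0.43) = 67%.

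*True methenamine rate at the margin (37%), 2 points under-recorded.* pT = 0.35, SE = √[(0.1716 + 0.2275)/120] = 0.0577. Error = Φ(0.02/0.0577 − 1.960) = Φ(−1.61) = 5.3%.

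| Assumed b | Power, equal true rates, over-recorded | One-sided error, truth at the margin, under-recorded |
|---|---|---|
| 0 | 80% | 2.5% |
| 1 point | 74% | 3.7% |
| 2 points | 67% | 5.3% |
| 3 points | 59% | 7.5% |

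Simulation of 400,000 trials at 0, 2 and 3 points agrees (2 points: 67.1% and 5.3%). Two points is 0.02 × 120 = 2.4 patients in the arm.

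**The case against.** Seeing a colour is not knowing a drug. The patient is not told what she takes, nothing says she sees the other products or a colour key, and the home dose is in a white vial or bag. The nurses who know the allocation do not decide the outcome, and the listed call topics do not include appearance. The symptom definition limits discretion, and culture-positive symptomatic UTI is already planned as a secondary comparison. All of this stands. A reader might infer that masking cannot hold; the documents support only that it is fragile and unprotected.

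A reader might also infer that handing back leftovers biases the primary outcome. It cannot affect symptoms reported or prescriptions written by day 21. It could colour only the UTI questions repeated at the late visit and the masking question itself. Nor does the protocol say that the physician receives or sees the returned drug.

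Nor do the two Yes answers on processing prove a contradiction. The item covers compounding as well as over-encapsulation, and capsules of different colours would be consistent with both statements. This is a point to reconcile.

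Finally, the word placebo survives in the Basic Info description and in the Procedures sentence on repeat catheter removal, which might suggest a dummy second dose. No such dose is described, and the sentence on the home dose limits it to methenamine and ciprofloxacin.

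What the objection does not answer is the second-dose question at levofloxacin sites, which needs no knowledge of colours and arises inside the window.

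**Conclusion.** The point holds in this form: masking is claimed but not secured, and its only described check is late and limited to patients. The strongest route is the compliance question at the levofloxacin sites; the colour difference applies at every site.

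The documents do not show that unmasking will occur, how often, or in which direction it would push the result, so no size of bias can be claimed. The calculation shows only that the design has little room: a net shift of 2 points in one arm costs about 13 points of power in one direction and roughly doubles the one-sided error in the other. It assumes a Wald comparison of risk differences at 120 per arm, a 15-point absolute margin, 22% in the fluoroquinolone arm, and a shift confined to the methenamine arm. This deserves correction because the remedies are cheap.

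**What to change.** 1. State in Procedures whether the drugs are over-encapsulated to look alike, and reconcile this with the two Yes answers on processing. If they are not, give each dose in an opaque cup or pouch and ask patients not to describe the medication or the number of doses to callers or physicians, without discouraging reports of side effects. Cost: wording and simple packaging. The documents do not establish that over-encapsulation is feasible, so the fix should not depend on it.
2. Have callers record the UTI symptom and treatment answers before any medication question, or move the compliance questions to the already-unmasked removal nurse. Reordering is free but protects only the current call, since a caller who has learned the arm carries it into the next one. Moving the questions protects all three calls, at the price of an extra contact.
3. Have leftovers returned in a sealed opaque envelope that the physician recording UTI answers does not see. This protects only the late retrospective answers and the masking check.
4. Add a treatment-guess question before the outcome is known, and keep the late one. The early question may prompt speculation and will miss later unmasking, so neither replaces the other.
5. If colour and number of doses remain distinguishable, report patients and callers as not reliably masked, and present the planned culture-positive UTI comparison beside the primary result. It is less subjective but not immune, because a culture is taken only from women who come forward with symptoms and is encouraged, not required.
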